**Primary endpoint:**

- A normalized urinary free cortisol level at week 4

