**Secondary endpoint:**

- A urinary free cortisol level above the upper limit of the normal range but reduced by  $\geq 50\%$  from baseline at week 4
- Plasma ACTH [ ] hour urinary free cortisol, serum and salivary cortisol levels over time
- Hemoglobin A1C (HbA1C), fasting blood glucose and blood electrolytes, e.g. K+
- Cushing's syndrome clinical signs and symptoms, e.g. weight, body mass index, blood pressure
- Changes in tumor size
- Safety end points: hematologic and blood chemistry including total sodium, potassium, urea, serum creatinine, creatinine clearance, total protein; LFT (ALT, AST, total bilirubin, albumin, ALP, [ ] total cholesterol (TC), LDL-cholesterol, triglycerides; coagulation (PT, INR) and ECG [ ]

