## **Section 7.0 Assessment of Efficacy**

The primary efficacy population will include patients who had baseline mean UFC levels 1.5x above the upper normal range, and who completed the 4-cycle, 4-week treatment period with no more than 2 weeks of interrupted drug doses. Baseline UFC levels are defined as the mean of three 24-hour urine specimens collected within one week of baseline visit.

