### *Primary outcome:*

- The primary efficacy outcome will be normalization of mean UFC levels after 4-weeks treatment. This will be measured as the mean of three 24-hour urine specimens collected at baseline and within 5 days before completion of the study. Patients who achieve a mean post-treatment UFC level within the normal range are considered responders.

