**Table 5. Adrenal Suppression Stopping Criteria**

Adrenal AE	Management/Next Dose for R-roscoxitine
24 hr UFC < LLN with signs or symptoms of adrenal insufficiency (fatigue, nausea, vomiting, abdominal pain and hypotension)	
 
• Hold IP for maximum 2 weeks
 
• Repeat 24 hr UFC in 1 week
 
• Discuss with DSMB the possibility of re-challenge with IP
 

24 hr UFC <LLN without signs or symptoms of adrenal insufficiency, and who can be monitored weekly	
 
• Continue IP
 
• Monitor weekly until 24 hr UFC stabilize, then monitor 24 hr UFC as per protocol assessment schedule
 

If the subject wants to continue for potential benefit of R-roscoxitine therapy after being informed of the results of 24 hr UFC testing, then the IP may be re-started at the reduced dose agreed upon by the investigator. 24 hr UFC and aforementioned signs and symptoms

should be monitored at a minimum of every week until resolution, stabilization, or a return to baseline values, at which point monitoring should be continued per protocol.

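### A mean post-treatment UFC below the lower limit of normal counts as non-response and also falls outside the ≥50% reduction endpoint, so the most suppressed patients are grouped with those who did not respond

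*Combined protocol and SAP*

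**What the plan says.** Section 4.0 gives the primary endpoint as "A normalized urinary free cortisol level at week 4" and does not define the term further. Section 7.0, Primary outcome, makes it operational with the average of three 24-hour collections: "Patients who achieve a mean post-treatment UFC level within the normal range are considered responders". Neither place says at or below ULN.

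The first secondary endpoint in Section 4.0 is a partial response. It begins "A urinary free cortisol level above the upper limit of the normal range but reduced by" and continues with a fall of at least 50% from baseline. A later item in the same list follows "hour urinary free cortisol, serum and salivary cortisol levels over time", without a response category.

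Table 5 in Section 8.0 shows that UFC has a lower limit in this protocol. It has one row for "24 hr UFC < LLN with signs or symptoms of adrenal insufficiency", with a hold of at most two weeks, and one for "24 hr UFC <LLN without signs or symptoms of adrenal insufficiency", where drug is continued under weekly monitoring. Section 7.0 admits to the primary efficacy population patients who "completed the 4-cycle, 4-week treatment period with no more than 2 weeks of interrupted drug doses", so patients from either row can be in the analysis.

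Section 9.0 calls the drug promising if three or more of 16 patients respond. It also plans a t test of serum cortisol or plasma ACTH between responders and non-responders. Nothing in the document says how a mean post-treatment UFC below LLN counts for efficacy.

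**The concern.** The two response categories do not follow the order of the drug's effect. Read literally, a patient can move from no response (little change), to partial response (halved but still above ULN), to response (in range), and back to no response (below LLN). In a trial meant to detect activity against cortisol excess, the last step groups marked suppression with absence of effect.

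Two analyses are exposed. The 3-of-16 rule turns on single patients, so one classification can decide the conclusion. In the Section 9.0 t test, strongly suppressed patients would sit in the non-responder group and pull the two group means together. Because the trial is open-label and the case is not addressed explicitly, there is also a risk that it is settled after the result is known.

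**Working it through.** **1. Classification.** Setting the definitions side by side:

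| Mean post-treatment UFC | Primary response (Section 7.0) | Partial response (Section 4.0) |
|---|---|---|
| Above ULN, fall under 50% | No | No |
| Above ULN, fall of 50% or more | No | Yes |
| LLN to ULN | Yes | Not applicable |
| Below LLN | No | No, because not above ULN |

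Illustration with an assumed baseline of 10×ULN and an assumed LLN of 0.1 to 0.2×ULN:
- To 5×ULN: 1 − 5/10 = 50% fall, partial response.
- To 0.5×ULN: 1 − 0.5/10 = 95% fall, response.
- To below 0.2×ULN: more than 1 − 0.2/10 = 98% fall, neither.

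**2. The plan's own figure.** Inputs from Section 9.0: n = 16, success at 3 or more responders, null rate 5%, target rate 25%, one-sided 0.05, power 80%. With X binomial,

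P(X ≥ 3) = 1 − Σ C(16,k) p^k (1−p)^(16−k), k = 0, 1, 2.

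- p = 0.05: 1 − (0.4401 + 0.3706 + 0.1463) = 0.0429.
- p = 0.25: 1 − (0.0100 + 0.0535 + 0.1336) = 0.8029.

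The design reproduces. Sixteen is also the smallest n that meets both limits; n = 15 with the same threshold gives power 0.7639.

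**3. Effect of the literal rule if 25% means at or below ULN.** Let s be the share of those patients who end below LLN. The countable rate is 0.25 × (1 − s). The documents give no value for s, so these are assumed values.

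| s | Countable rate | Power | Loss (points) | Expected such patients, 16 × 0.25 × s |
|---|---|---|---|---|
| 0% | 25.0% | 80.3% | 0 | 0 |
| 5% | 23.75% | 77.0% | 3.3 | 0.2 |
| 10% | 22.5% | 73.3% | 7.0 | 0.4 |
| 20% | 20.0% | 64.8% | 15.5 | 0.8 |

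A single patient decides the result when exactly three reach ULN or below. At 25% that has probability C(16,3) × 0.25³ × 0.75¹³ = 0.208. One of the three ending below LLN would then bring the count to two.

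**4. If 25% means within range.** Power is 80.3% whatever the below-LLN share. The caution then runs the other way. If the 5% null rate is also meant for the within-range definition, moving the cut to ULN without revisiting it could raise the false-positive rate. With a further 1.25% or 2.5% of patients below LLN under the null (assumed), the rate at or below ULN is 6.25% or 7.5%, and P(X ≥ 3) is 0.0742 or 0.1135 instead of 0.0429. This is why the two rates must be tied to the chosen definition.

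**The case against.** The strongest reply is that the document speaks throughout of normalization: in the hypothesis, the objective, the endpoint and the statement of benefit. In-range is the ordinary meaning of that word. Table 5 places UFC below LLN among adrenal adverse events, so withholding credit for it is a coherent and conservative choice. Urine is self-collected, and a very low value may reflect an incomplete collection, which a rule without a lower bound would score as success. These points stand. They are the reason to keep the strict rule as a sensitivity count. They do not explain why the same patient also falls outside partial response, or why the responder comparison should treat that patient as unresponsive.

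A reader might infer several stronger things that the documents do not support:
- **That the trial is underpowered or its response rate biased downward.** This needs the 25% to refer to UFC at or below ULN, which Section 9.0 does not say, and a below-LLN share, which the documents do not give.
- **That such patients are declared treatment failures.** The document only separates those who respond from those who do not.
- **That a value below LLN is the largest possible fall.** That depends on baseline. With LLN assumed at 0.1 to 0.2×ULN, going from 1.5×ULN to LLN is a fall of 87% (1 − 0.2/1.5) to 93% (1 − 0.1/1.5), less than the 95% of the in-range example above.
- **That Table 5 predicts this outcome at the end of treatment.** It is conditional and covers a UFC result at any time. The responder rule uses an average of three collections, so one low specimen does not by itself make a non-responder.
- **That the information is lost.** UFC over time and the regression of end-of-study on baseline UFC keep the value; neither feeds the 3-of-16 decision.

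**Conclusion.** The point holds as a defect of endpoint classification. On the literal text, a mean post-treatment UFC below LLN is a non-response and is outside the partial-response endpoint, while a smaller fall from the same baseline that stays above ULN earns partial credit. This follows from the wording alone and needs no assumption.

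Its numerical size does rest on assumptions. If the 25% target means UFC at or below ULN, power falls from 80.3% to 77.0%, 73.3% or 64.8% for assumed below-LLN shares of 5%, 10% or 20%. If the 25% means within range, there is no loss. The sample size calculation is sound, and it should not be inferred that 16 patients or the threshold of three is wrong. The change is worth making because the case is foreseeable, the decision rests on few patients, and the remedy is cheap.

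**What to change.** - In Sections 4.0 and 7.0, define biochemical response as mean post-treatment UFC at or below ULN, and use the same definition for the responder analyses in Section 9.0.
- In Section 9.0, confirm that the 5% and 25% rates refer to that definition. If they do, n = 16 and the threshold of three stand. If they were set for the within-range definition, restate them and recheck the rule.
- Report patients with mean UFC below LLN on a separate line, so that over-suppression or a suspected incomplete collection is visible.
- Give a sensitivity count under the strict within-range rule, with below-LLN patients as non-responders, and state whether the 3-of-16 conclusion changes.

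The cost is a few sentences in three sections and one extra line in the results; no new data are needed. The downside is that an over-suppressed patient, or one with an incomplete collection, would count as a success in the main analysis. The separate line and the sensitivity count expose that. Should the sponsor prefer to keep the within-range rule deliberately, the plan should say so and state how below-LLN patients are classed for partial response. None of this bears on how such patients are managed.

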### *Secondary outcome:*

- Plasma ACTH, serum cortisol levels will be measured at baseline, day 1, 8, 15, 22 and 29 every 3 hours from 9:00–15:00. The areas under the concentration-time curve (AUC0–8h) for ACTH and cortisol will be calculated using a trapezoidal method from 0–6 h (the last sampling time point) by WinNonlin software (Pharsight, Mountain View, CA). Visual field will be measured at baseline and end of the study.

## **Section 8.0 Assessment of Safety**

Cross reference: [IND No. 71,011-CYC202(R-roscoxitine or Seliciclib)].

### ***Monitoring for adverse effects (further detailed below):***

- Patients will be seen in clinic every week and evaluated for adverse effects with physical exam, ECG, chemistry, hematology panels, as listed in Table 1. Adverse events will be graded according to NCI Common Terminology Criteria (NCI-CTCAE). Known common adverse events of R-roscoxitine at 400mg oral dose twice daily include fatigue, fever, nausea, vomiting, anorexia, hepatic dysfunction (increased ALT/SGPT, AST/SGOT and AP), hypokalemia, hyponatremia, anemia and insomnia (cross reference: IND No. 71,011-CYC202(R-roscoxitine or Seliciclib)).
- 
- If at any time a patient demonstrates a worsening of their visual fields or tumor growth on MRI, they will be withdrawn from the study and referred for surgery.
- All patients will be followed regularly until the resolution or stabilization of drug-related toxicity. A post-treatment follow-up visit will be conducted within 4 weeks after the last dose of the study drug or prior to the initiation of new treatment. This post-treatment evaluation may be conducted over the telephone if the patient is unable to return to the clinic.
- In all cases where the subject is withdrawn due to unusual or unusually severe adverse event considered related to R-roscoxitine, the withdrawal will be reported as an SAE and on the CRFs.

### ***Dose delays and dose reductions:***

- Dose delay or reduction for drug-related toxicity is permitted; however the DSMB will be consulted prior to implementing any change in dosing. Dose delay or reduction will only be implemented when all supportive care measures have been exhausted without an improvement of patient status.
- Those subjects with toxicity less than or equal to NCI-CTCAE Grade 2 will continue their full dose, unless the investigator, based on clinical judgment, feels it is necessary to have their dose reduced or held.
- Patients experiencing unacceptable toxicity (Grade 3 or higher) that the investigator considers directly attributable to R-roscovitine should have their dose held, reduced, or should be withdrawn from the study (**Table 2 and 3**).
- Treatment may be delayed, up to 2 weeks, until the patient recovers completely or the adverse event reverts to Grade 1 or to baseline grade.
- A maximum two dose reductions are permitted per subject and subjects will not be re-challenged to a higher dose level.
- The Investigator will consult the DSMB prior to continuing therapy for any subject requiring a delay of more than 2 weeks for unresolved toxicity, but in general, such subjects should be withdrawn from the study.

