**Table 2. Guideline for Dose Modifications**

Patients	Adverse event	Action
All	Grade $\leq$ 2 (mild to moderate)	No drug dose adjustments*
	Grade 3 (severe)	Hold the dose for a maximum of 14 days until the patient recovers completely or the adverse event reverts to $\leq$ Grade 1 or to baseline grade. Resume at one dose level lower ( Table 3 ). If AE recurs at grade 3, reduce dose by 200 mg q.d. again and maintain at lower dose. If AE does not improve to grade $\leq$ 2 within 1 week on 200 mg b.i.d., patient is to discontinue treatment. 
	Grade 4 (life-threatening)	Discontinue study drug

\*Unless the investigator, based on clinical judgment, feels it is necessary to have dose reduced or held.

Note: for hepatic safety management follow ***Liver Chemistry Stopping and Follow up Criteria***

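### Section 8.0 requires DSMB consultation and exhausted supportive care before any toxicity-related delay or reduction, with no exception for the Grade 3 hold in Table 2

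*Combined protocol and SAP*

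**What the plan says.** The first bullet of Dose delays and dose reductions (Section 8.0) permits delay or reduction for drug-related toxicity on two conditions. First, "the DSMB will be consulted prior to implementing any change in dosing". Second, "Dose delay or reduction will only be implemented when all supportive care measures have been exhausted without an improvement of patient status".

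Later bullets in the same list give instructions by grade:

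- At Grade 2 or lower, patients stay on full dose "unless the investigator, based on clinical judgment, feels it is necessary to have their dose reduced or held".
- Patients with toxicity of Grade 3 or higher "that the investigator considers directly attributable to R-roscovitine should have their dose held, reduced, or should be withdrawn from the study".
- A delay may last up to 2 weeks, until full recovery or a return to Grade 1 or baseline grade.
- For long delays, "The Investigator will consult the DSMB prior to continuing therapy for any subject requiring a delay of more than 2 weeks for unresolved toxicity".

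The Grade 3 row of Table 2 begins: "Hold the dose for a maximum of 14 days until the patient recovers completely". It then restarts the patient one dose level lower. Table 2 has one footnote, on investigator judgment at the lower grades, and one note, which sends liver events elsewhere ("Note: for hepatic safety management follow" the liver criteria).

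Three organ-specific rules work differently. Tables 4 (liver) and 5 (adrenal) list the hold first and bring in the DSMB at re-challenge. The dermatologic subsection allows an interruption of up to 14 days and mentions no DSMB step.

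**The concern.** The two conditions in the first bullet are mandatory and carry no exception for grade or urgency. An investigator facing a drug-related Grade 3 event therefore has two instructions that cannot both be followed at once. One is to hold the dose. The other is to consult the DSMB first and to hold only after supportive care has failed. Nothing states which prevails.

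What is at stake is patient safety: a patient with severe drug-related toxicity could continue dosing while supportive care is tried and the DSMB is reached. An investigator who holds immediately protects the patient but departs from the first bullet.

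**Working it through.** This is mainly a check of text against text, with one simple bound on exposure.

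**1. Do the conditions reach the Table 2 hold?** The DSMB clause covers any dosing change, so it reaches a hold directly. The supportive-care clause speaks of delay or reduction, so it reaches a hold only if a hold is a delay. The delay bullet and the Grade 3 row of Table 2 match on both features:

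| Feature | Delay bullet | Table 2, Grade 3 hold |
|---|---|---|
| Maximum length | 2 weeks | 14 days |
| Ends when | full recovery, Grade 1 or baseline grade | full recovery, Grade 1 or lower, or baseline grade |

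They describe the same action, so both conditions apply to the hold.

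**2. Is there an exception?** The Grade 3 bullet, Table 2 with its footnote and note, Section 4.0 (Intervention), Section 5.0 (Withdrawal of Subjects), Tables 3 to 5 and the dermatologic subsection were read for one. None exempts the Table 2 Grade 3 hold, and none sets an order of precedence.

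**3. Where does the protocol place the DSMB elsewhere?**

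| Place | DSMB step |
|---|---|
| First bullet, Dose delays and dose reductions | before any change |
| Last bullet of that list (toxicity delay over 2 weeks) | before continuing |
| Text after Table 3 (other delays over 2 weeks) | before continuing |
| Table 4, hold row | at re-challenge, after the hold |
| Table 5, symptomatic row | at re-challenge, after the hold |

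Only the first bullet puts the DSMB before the protective step.

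**4. Who is exposed?** Start from drug-related Grade 3 toxicity. Remove events covered by Table 4, Table 5 and the dermatologic subsection. Remove patients who are withdrawn, because withdrawal is neither a delay nor a reduction. Grade 4 is outside the group because Table 2 and Section 5.0 discontinue the drug.

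**5. How much extra drug?** Section 4.0 gives 4 dosing days a week for 4 weeks: 4 × 4 = 16 planned dosing days. A delay of one week adds at most one block: 4 / 16 = 25% of the planned dosing days. Each week has 7 − 4 = 3 drug-free days, so a short wait that falls within them adds none. The range per week of delay is therefore 0 to 4 dosing days. The expected value would need a Grade 3 rate and a DSMB response time, and the documents give neither.

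**The case against.** The strongest reply is that ordinary reading settles the matter. The Grade 3 bullet and Table 2 are specific and directive, the first bullet is general, and a sensible site would hold at once. The DSMB has only to be consulted, not to approve, so that step could be quick. Treating a hold as a delay is also an inference. Much of this stands: immediate action was probably intended. But the inference is well supported by the matching limits, Table 2 is titled a guideline while the first bullet is mandatory, and the supportive-care condition is not met by a quick call.

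Four stronger readings are tempting and are not supported:

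- A reader might infer that the plan deliberately keeps patients with Grade 3 toxicity on drug. The Grade 3 bullet and Table 2 point the other way; this is an unreconciled conflict.
- A reader might infer a direct contradiction with investigator judgment at Grade 2 or lower, or with the reduction allowed at any time in Section 4.0. Both can be read alongside the conditions: one says when full dose need not continue, and the other is a permissive summary that Section 8.0 details.
- A reader might take the list of known common events in Section 8.0 as a measure of how often the problem arises. That list gives event types without grade, so it says nothing about Grade 3 frequency.
- A reader might infer a loss of power, because Section 7.0 requires completion of the 4-week treatment period and a patient withdrawn instead of held leaves the primary efficacy population. Withdrawal for any reason has that effect, so it cannot be attributed to this rule.

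**Conclusion.** The point holds as a bounded drafting conflict in a safety rule, and it should be fixed. Followed as written, the first bullet can delay the Grade 3 hold that Table 2 prescribes.

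The conclusion rests on two things: reading a hold as a delay, and the absence of any precedence rule. Its size is limited to the group in step 4 and to the bound in step 5. That bound assumes the planned weekly schedule is followed. How often the situation would arise is unknown from the documents.

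**What to change.** In Dose delays and dose reductions, replace the two conditions with:

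> The investigator may hold, reduce or stop the dose immediately for safety. For Grade 3 toxicity the dose is held at once per Table 2 (or the patient is withdrawn), the DSMB is notified promptly, and the DSMB is consulted before dosing resumes at the lower level. For Grade 2 or lower toxicity, supportive care is tried first where appropriate, but the investigator may hold or reduce on clinical judgment and then notify the DSMB.

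Three matching edits are needed:

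- Change the Grade 3 bullet to hold or withdraw, with any reduction made at restart. Table 2's Grade 3 row has no attribution limit, so the replacement text has none either.
- State that the lower-level restart in Table 2 also applies to Grade 3 skin events. The dermatologic subsection now reinstates the daily dose and does not mention a lower level.
- In Section 4.0 (Intervention), keep the reduction at any time and add that it follows Section 8 and Tables 2 and 3.

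Keep Grade 4 discontinuation, Tables 4 and 5, and the last bullet on delays of more than 2 weeks.

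The cost is an amendment of wording only, with no change to sample size, visits or analysis. The downside is that the DSMB reviews a hold after it starts rather than before; it still reviews before restart.

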**Table 2. Guideline for Dose Modifications**

Patients	Adverse event	Action
All	Grade $\leq$ 2 (mild to moderate)	No drug dose adjustments*
	Grade 3 (severe)	Hold the dose for a maximum of 14 days until the patient recovers completely or the adverse event reverts to $\leq$ Grade 1 or to baseline grade. Resume at one dose level lower ( Table 3 ). If AE recurs at grade 3, reduce dose by 200 mg q.d. again and maintain at lower dose. If AE does not improve to grade $\leq$ 2 within 1 week on 200 mg b.i.d., patient is to discontinue treatment. 
	Grade 4 (life-threatening)	Discontinue study drug

\*Unless the investigator, based on clinical judgment, feels it is necessary to have dose reduced or held.

Note: for hepatic safety management follow ***Liver Chemistry Stopping and Follow up Criteria***

